Sub-dissociative Dose Ketamine Dosing Study

NCT03714620

Date 10/17/2018

I. Study Protocol

Patient screening, enrollment, and data collection will be performed by the study investigators. All adults ≥ 18 years of age and < 60 years of age and weighing between 45-115 kg with acute abdominal, flank, back, musculoskeletal pain, or headache, with a score of 5 or more on a standard 11-point (0 to 10) VAS pain rating scale requiring intravenous analgesia, as determined by the treating attending physician, will be screened for inclusion. Exclusion criteria are as follows: pregnancy, breast-feeding, altered mental status rendering the patient unable to consent to the study, allergy to ketamine, unstable vital signs (systolic blood pressure <90 or >180 mm Hg, pulse rate <50 or >150 beats/minute, and respiration rate <10 or >30 breaths/minute), and medical history of acute head or eye injury, seizure, intracranial hypertension, chronic pain, renal or hepatic insufficiency, history of alcohol or drug abuse, and psychiatric illness. Only the first admission will be included if patients present multiple times during the study period.

i. Recruitment procedures

1. Where will recruitment occur?

Recruitment will occur in the LUMC ED upon patient's arrival and once physician has deemed it necessary that the patient receive intravenous pain medication.

2. Where and when will consent be obtained?

Consent will be obtained in the Emergency Department once it is determined that the patient meets inclusions criteria for enrollment if the patient is able to provide it.

3. Who will obtain consent?

The treating attending physician, or one of physician members of the research team, will obtain consent from the patient in the ED.

ii. Screening procedures

Patients will be screened as a convenience sample during daytime hours Monday – Friday when any of the study investigators are working and the ED clinical pharmacist is available to prepare the study drug and randomize the patients. Patients presenting to the ED with acute moderate to severe abdominal, flank, back, musculoskeletal pain, or a headache will be screened for inclusion criteria and asked to consent prior to enrollment. Consent must be obtained prior to enrollment.

b. Randomization procedures (if applicable)

The study will be double-blinded and randomized. Patients meeting inclusion criteria who consent for participation will be randomized in a 1:1 fashion to either Ketamine 0.15 mg/kg IVBP or Ketamine 0.3 mg/kg IVBP. Dosing will be based on actual body weight. Both drugs will be administered over 15 minutes. Physicians will obtain consent from the patient, but will not be aware of dose that the patient receives. Treatment will be prepared and blinded by the ED clinical pharmacist. ED Pharmacist will maintain the randomization list, which was generated before commencement of the study, prepare the medication, and deliver it to the nurse caring for the study participant in a blinded manner.

c. Study Intervention

i. For Drug/device studies:

1. Active study agents

Ketamine 0.15 mg/kg IVBP administered over 15 minutes

Ketamine 0.3 mg/kg IVBP administered over 15 minutes

2. Placebo study agents

No placebo

3. Blinding/labeling/preparation of agents

Patients will be randomized in a 1:1 fashion to receive either 0.15 mg/kg of Ketamine IVPB or 0.3 mg/kg of Ketamine IVBP. The ED clinical pharmacist will prepare and label the study treatments, and ensure blinding of the patient, research team, and clinical staff.

4. Storage

Storage of the study medication will be kept in the ED pyxis to facilitate rapid use.

5. Administration

0.15 mg/kg or 0.3 mg/kg dose of Ketamine administered intravenously over 15 minutes

6. Toxicities and guidelines for adjustments

No dosage adjustment will be necessary.

ii. For Other types of intervention studies: n/a

1. Active intervention description

2. Control group

d. Study Assessments and Activities

i. Describe all study procedures, assessments, and subject activities

Patients will be consented for participation by one of the study investigators or the treating ED attending physician. The ED pharmacist will prepare the medication, and ensure blinding of the patient, research team, and clinical staff. The nurse caring the patient will administer the IV medication and give the patient a survey to fill out regarding pain relief and side effects at 15 minutes, 30 minutes, and 60 minutes post initiation of administration of the ketamine. Time zero will be time the drug administration is initiated. The survey will ask the patient to rate their pain using the VAS pain rating scale. Additionally, it will have a list of adverse effects, and the patient will need to rate each adverse effect using a 5 point SERSDA scale (rating each adverse event from “absent” to “very bothersome”). At the same time intervals (15, 30, and 60 minutes post initiation of drug administration), the nurse will rate the patient using the RASS scale. Vital signs will be monitored per ED protocol. Rescue analgesia will be offered at 30 minutes.

ii. Provide a schedule of all study assessments and subject activities, including a tabular representation or timeline as applicable

-Patient presents to the emergency department with acute pain

-Emergency treatment will not be delayed for the purposes of this study

-Patient seen by physician and screened for inclusion/exclusion criteria

-Patient consented for participation by research team member or physician treating the patient

-Patient randomly assigned to treatment group

-Drug prepared by ED pharmacist, administered by blinded nurse

-Time zero (0) is when nurse initiates administration of the ketamine

-Ketamine infuses over 15 minutes, ending at 15 min time mark

- Survey administered to the patient to be filled out at 15 min, 30 min and 60 min post administration of the ketamine (nurse to alert patient at specified time intervals)
- Nurse to score patient using RASS scale at 15 min, 30 min, 60 min post initiation of drug administration

II. Safety Monitoring Plan

- a. Definition of adverse events, serious adverse events

Adverse effects include dizziness, disorientation, dysphoria, nausea. Adverse events include hypoxia (<90%), hypotension (<90 systolic), vomiting, or life-threatening events.

- b. What procedures will be used to monitor subject safety?

Ketamine is currently being used in sub-dissociative doses in the ED at LUMC to treat acute pain utilizing doses between 0.1 mg/kg- 0.3 mg/kg. The procedures to monitor safety are consistent with the ED guidelines used in current practice at LUMC. Subjects will have continuous telemetry monitoring including heart rate, respiratory rate and oxygen saturation. Vital signs (including but not limited to blood pressure measurements) will be measured and documented per standard protocol in the ED. Documented adverse side effects of sub-dissociative ketamine have included dizziness, dysphoria, and disorientation, but no serious adverse events have been noted.

- c. Who (list names) will identify, document, and report adverse events?

The blinded physician, nurse caring for patient, or one of the research team members, will identify, document, and report adverse events.

- d. What is the frequency for review of summarized safety information and who will perform the review (e.g., safety monitoring board)?

The research team will review safety information weekly.

- e. What are the stopping rules with regard to efficacy and safety?

As the target enrollment is 49 subjects per group, and we see hundreds of adult patients monthly for acute pain, we do not anticipate needing to stop the trial early. All adverse events will be reviewed and the study will be stopped immediately if we determine the AE was directly related to the subject's participation in the study.

III. Analysis Plan

Describe statistical analysis methods as appropriate. For example, will intention-to-treat methodology be used in the analysis? Will there be any sample stratification?

Descriptive statistics, including means, standard deviations, medians, interquartile ranges and percentages will be calculated for baseline variables. Comparisons of continuous parametric variables will be done using a t test. Non-parametric data will be expressed as a median and analyzed using the Mann-Whitney test. A Chi-square test or Fischer's exact test will be used to compare categorical variables as appropriate. A bivariate analysis will be performed to assess differences between SDK regimens. A P value < 0.05 will be considered significant. Microsoft Excel software and STATA version 12 will be used for data analysis.

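### No side-effect rating is scheduled before dosing, so nausea or dizziness already present cannot be separated from drug effects with the planned data

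*Combined protocol and SAP*

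**What the plan says.** Section I.d.i has the nurse "give the patient a survey to fill out regarding pain relief and side effects at 15 minutes, 30 minutes, and 60 minutes post initiation" of the infusion. On that survey the patient is to "rate each adverse effect using a 5 point SERSDA scale". The schedule in I.d.ii lists the same times: "Survey administered to the patient to be filled out at 15 min, 30 min and 60 min post administration of the ketamine". Time zero is the start of the infusion. Neither place lists a side-effect rating between consent and time zero. The only pre-dose score implied anywhere is the pain VAS used for eligibility in Section I.

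Eligible complaints are "acute abdominal, flank, back, musculoskeletal pain, or headache", and no exclusion covers nausea or dizziness at presentation. Section II.a states: "Adverse effects include dizziness, disorientation, dysphoria, nausea". It does not require the symptom to be new or worse. Section I.c states that there is no placebo. Section III summarises baseline variables without listing them and plans a bivariate comparison of the two regimens, with no adjustment mentioned. Target enrolment is 49 per group (II.e).

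**The concern.** Abdominal pain, flank pain and headache can bring nausea or dizziness with them. A patient who is nauseated on arrival and still nauseated at 15 minutes would rate nausea as present. On post-dose ratings alone, that patient looks the same as one made nauseated by ketamine. With no placebo arm, there is no background rate to set against the observed one.

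Two things are at stake. The first is how the per-arm nausea and dizziness rates can be read. If all post-dose ratings are counted, these rates mix presenting symptoms with drug effects. The second is chance imbalance between the arms in pre-dose symptoms, which at this sample size is not rare and could be neither seen nor adjusted for.

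The point covers nausea and dizziness only. It concerns symptoms present before dosing, not illness symptoms that begin afterwards.

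**Working it through.** The plan gives no side-effect rate and no basis for 49 per group, so there is no figure of its own to reproduce.

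**Inputs.** From the documents: 49 per arm, 1:1 allocation, significance at 0.05 (taken as two-sided). Assumed: b, the share with the symptom before dosing, 10% or 20%; p, the drug-induced rate, 10% to 70%; and the share of pre-dose symptoms that persist. A symptom has cleared if it is absent at 15, 30 and 60 minutes. Persistence is uncertain, partly because "Rescue analgesia will be offered at 30 minutes".

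**1. Per-arm rate.** Let e = b × share persisting. If every post-dose rating counts, the observed rate is e + (1−e)p, so the overstatement is e(1−p).
- All persist: smallest 0.10 × 0.30 = 3 points; largest 0.20 × 0.90 = 18 points.
- Half clear: smallest 0.05 × 0.30 = 1.5 points; largest 0.10 × 0.90 = 9 points.

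**2. Chance imbalance.** With two independent Binomial(49, b) counts, the probability that they differ by 5 or more (5/49 = 10 points) is 0.127 at b = 10% and 0.254 at b = 20%. If those symptoms persist, a difference of 5 patients moves the observed dose difference by (5/49)(1−p): 3.1 points at p = 70% and 9.2 at p = 10%.

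**3. Power (secondary).** The table uses the pooled two-proportion formula at b = 20%. Present/absent counts all 49 per arm. New onset uses the 49 × 0.8 = 39.2 per arm who are symptom-free before dosing.

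| Drug-induced rates | Present/absent, all persist | Half clear | Three quarters clear | New onset |
|---|---|---|---|---|
| 10% vs 30% | 0.377 | 0.510 | 0.598 | 0.603 |
| 30% vs 60% | 0.672 | 0.771 | 0.816 | 0.772 |
| 40% vs 70% | 0.703 | 0.786 | 0.824 | 0.772 |

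New onset gains 7 to 23 points if all symptoms persist and can lose up to 5 if most clear.

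Present/absent stratified by pre-dose symptom (Mantel-Haenszel, simulated, b = 20%) keeps all patients. For the three pairs in the same order, stratified against unstratified power is:
- all persist: 0.616 vs 0.373, 0.773 vs 0.685, 0.771 vs 0.702;
- half clear: 0.573 vs 0.513, 0.793 vs 0.785, 0.800 vs 0.788;
- all clear: 0.712 vs 0.726, 0.857 vs 0.865, 0.856 vs 0.864, a loss of at most 1.4 points.

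Plain change from pre-dose does poorly when symptoms clear. In simulated Mann-Whitney tests with b = 20%, three quarters clearing and 10% vs 30%, power is 0.427, against 0.600 for the raw post-dose score.

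**4. Does an all-patient new-or-worse rate repair the per-arm figure?** Assume severity is split 40/30/20/10% over the four non-absent grades, for both pre-dose and drug-induced symptoms, and that the post-dose score is the higher of the persisting and the drug score. The chance that the drug score exceeds the pre-dose score is (1 − 0.16 − 0.09 − 0.04 − 0.01)/2 = 0.35. The new-or-worse rate is then too low by b × p × 0.65. At b = 20% and p = 70% that is 0.20 × 0.70 × 0.65 = 9.1 points. The raw rate there is too high by 0.20 × 0.30 = 6 points if all persist, or 3 if half clear. At p = 10% with all persisting, the errors are 1 point too low against 18 too high. So this rate helps when p is low and can do harm when p is high. The rate among patients without the symptom before dosing estimates p without either error.

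**The case against.** The strongest objection is that the only inferential aim in Section III is to compare the two regimens, and randomisation already protects that comparison. Absolute per-arm rates are not a declared objective. This stands, and it limits the weight of the point. It does not remove it: side effects are one of the two things the patient survey measures, and their rates will be read as rates due to ketamine.

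A reader might go further and infer that the plan counts pre-existing nausea or dizziness as a side effect. The documents do not say so. They give no rule for scoring or summarising the SERSDA ratings, Section II.a only names the effects, and the survey form is not included, so its wording may ask about attribution. What the documents support is that the scheduled ratings alone cannot separate earlier symptoms from new ones.

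A reader might also infer that the loss can never be repaired. That is too strong. A simple record of whether the symptom was present before dosing would serve for stratification, and the documents do not say what is charted or which baseline variables are kept. But nothing in the plan secures such a record.

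Finally, b, p and persistence are all assumed, and the effect on power changes sign across plausible values. That also stands, so power is not the argument for the change.

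**Conclusion.** The concern holds as a cheap improvement. It is not a flaw in the validity of the dose comparison, which stays unbiased. Without a scheduled pre-dose rating, the nausea and dizziness rates in each arm would be overstated by 3 to 18 points if symptoms persist, or 1.5 to 9 if half clear. This assumes b of 10% to 20%, p of 10% to 70%, and that all post-dose ratings are counted. An imbalance of five or more symptomatic patients between arms has probability 13% (b = 10%) or 25% (b = 20%) and would go unseen and unadjusted. These figures show what is possible; they are not findings about this trial. Any gain in power is secondary and depends on how many pre-dose symptoms persist.

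**What to change.** 1. In I.d.i and I.d.ii, add one use of the existing survey just before time zero. The schedule already has a step where it could fit ("Drug prepared by ED pharmacist, administered by blinded nurse"), for example while the drug is being prepared. It must respect the rule that "Emergency treatment will not be delayed for the purposes of this study".
2. Report per arm the pre-dose prevalence of each symptom, and the post-dose rate among patients without that symptom before dosing.
3. If an all-patient new-or-worse rate is also shown, state that it understates drug effects in patients who already had the symptom.
4. In Section III, name one dose comparison in advance. Either use present/absent after dosing stratified by pre-dose symptom (Mantel-Haenszel), which keeps every patient and loses little if symptoms clear, or use new onset among patients without the symptom before dosing (chi-square or Fisher). Both condition only on a pre-dose rating, so the randomised comparison is kept. Do not use plain change from pre-dose.

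The cost is four surveys per patient instead of three, or 2 × 49 = 98 extra forms, given by the same nurse. The downside is one more short form for a patient in pain. No new instrument, staff or procedure is needed.

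### Does the schedule time the pain and side-effect survey from the end of the infusion, 15 minutes later than the rest of the protocol?

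*Combined protocol and SAP*

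**What the plan says.** Section I.d.i has patients complete the survey (VAS pain score and SERSDA side-effect ratings) "at 15 minutes, 30 minutes, and 60 minutes post initiation of administration of the ketamine". It then fixes the clock: "Time zero will be time the drug administration is initiated". It places the nurse's RASS rating at the same three times as the survey, and adds "Rescue analgesia will be offered at 30 minutes" without restating where that 30 minutes begins.

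Section I.d.ii lists the same activities in order, and four consecutive entries matter. The first repeats the definition of the clock: "Time zero (0) is when nurse initiates administration of the ketamine". The second places the end of the infusion on that clock: "Ketamine infuses over 15 minutes, ending at 15 min time mark". The third is the survey line at issue, which reads "Survey administered to the patient to be filled out at 15 min, 30 min and 60 min post administration of the ketamine". The fourth, on RASS, reads "Nurse to score patient using RASS scale at 15 min, 30 min, 60 min post initiation of drug administration".

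The third entry, on the survey, lacks the word initiation. The fourth has it, as does the survey sentence in I.d.i.

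**The concern.** For a bolus the missing word would hardly matter. Here the drug runs over 15 minutes, so the start and the end of administration are different moments. Two neighbouring schedule lines carry the same three numbers but different anchor words, and a reader could take the difference as deliberate.

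If the survey were timed from the end of the infusion, three things would follow. No pain or side-effect rating would be taken as the infusion finishes. The survey and RASS would no longer describe the same moment. The score labelled 30 minutes could be taken after rescue had been offered, so it would no longer reflect the study dose alone. If some nurses used one clock and some the other, scores from different times would be pooled under one label. The survey carries the patient-reported data on which the two doses would be compared, so the point deserved a check.

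**Working it through.** **Inputs.** Infusion length is 15 minutes in both arms (Randomization procedures; Study Intervention). Time zero is the start of administration (I.d.i and I.d.ii). Nominal survey and RASS times are 15, 30 and 60 minutes (I.d.i and I.d.ii). Rescue is offered at 30 minutes (I.d.i), with the anchor not restated. Target enrolment is 49 per group (Safety Monitoring Plan).

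**Two readings of the survey line, in minutes after time zero.**

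| | Survey | RASS | Gap to RASS |
|---|---|---|---|
| A: from start of infusion | 0+15 = 15, 0+30 = 30, 0+60 = 60 | 15, 30, 60 | 0 |
| B: from end of infusion | 15+15 = 30, 15+30 = 45, 15+60 = 75 | 15, 30, 60 | 15 at each time |

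Under B, with rescue counted from time zero, the second survey falls 45 − 30 = 15 minutes after the rescue offer. If rescue were also counted from the end of infusion, it would fall at 15 + 30 = 45 and coincide with the second survey again.

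**Which reading the documents support.**

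1. I.d.i times this same survey explicitly from the start.
2. I.d.i defines time zero as the start, and the schedule repeats that definition two lines above the survey line.
3. The line between them places the end of infusion at the 15-minute mark, so the schedule is already using the start-of-infusion clock when the survey line is reached.
4. I.d.i gives RASS and the survey common times. Reading B breaks that link; reading A keeps it.
5. No sentence times the survey from the end of infusion.

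Five points favour A. Only the missing word favours B.

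**If some nurses nevertheless used B.** Let a share p of patients be surveyed 15 minutes late. The standard deviation of survey timing is 15 × √(p(1 − p)), which is largest at p = 0.5: 15 × 0.5 = 7.5 minutes. Allocation is random and the nurse is blinded, so the expected difference in mean timing between arms is zero. In that worst case its standard error is 7.5 × √(2/49) = 7.5 × 0.202 ≈ 1.5 minutes. The result is noise shared by both arms, with no built-in advantage to either dose.

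The documents give no effect size, standard deviation, rescue uptake or primary time point, so this timing noise cannot be converted into points on the pain scale.

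**The case for a change.** The best case for a change is practical. The survey line is an instruction to the nurse, who starts the infusion and prompts the patient, and it names its own anchor instead of referring to time zero. The protocol does not describe recording when each survey was actually completed, so a nurse on the wrong clock could not be identified later. Correcting the wording costs almost nothing.

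Part of this stands: the line is loosely worded, and a hurried reader taking it in isolation could misread it. The rest does not carry far. The documents do not say which text, form or training the nurses use, and the survey form is not shown, so it is not established that this line governs practice. The Analysis Plan (section III) names no primary time point, describes no analysis that pairs survey scores with RASS, and uses no actual completion times. Recording them would be an added preference with no demonstrated gain.

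The rescue argument is weaker still. On the start-of-infusion clock the 30-minute survey and the rescue offer already share a nominal minute with no stated order, and the last survey follows the offer on either clock. Whatever rescue does to the later scores is a separate question, which this line neither creates nor settles.

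**Conclusion.** No change to the plan follows. The survey line contains a clerical slip, and the intended timing is recoverable from the protocol itself: 15, 30 and 60 minutes after the infusion starts, with a gap of 0 minutes to RASS. The 15-minute shift to 30, 45 and 75 minutes is correct arithmetic, but it arises only on a reading that conflicts with the schedule's own time zero and with I.d.i. Supplying the missing word would leave every planned assessment and analysis as it is.

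This rests on staff following the stated time zero. If some did not, the likely cost is timing variability common to both arms, with a standard deviation of at most 7.5 minutes, and not bias between doses. The 15-minute overlap with rescue also requires the rescue offer to be counted from time zero, which its sentence does not state.

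### II.e halts the whole study after any single adverse event judged directly related to participation, and II.a sets no seriousness tier, so one related non-serious event such as vomiting could stop the trial before 98 patients

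*Combined protocol and SAP*

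**What the plan says.** Section II.e is the only place where the protocol sets a stopping rule. It says "All adverse events will be reviewed" and that "the study will be stopped immediately if we determine the AE was directly related" to the subject's participation. What stops is the study, not one patient's infusion. The trigger is one event, and no number, rate, grade or seriousness is attached to it.

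Section II.a gives two lists under a heading that promises definitions of both adverse events and serious adverse events. The first reads "Adverse effects include dizziness, disorientation, dysphoria, nausea". The second reads "Adverse events include hypoxia (<90%), hypotension (<90 systolic), vomiting, or life-threatening events". Neither list is labelled serious.

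Three other statements bear on the rule:

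- II.e, after giving the target of 49 per group, continues "and we see hundreds of adult patients monthly for acute pain, we do not anticipate needing to stop the trial early".
- II.b reports that sub-dissociative ketamine at 0.1 to 0.3 mg/kg is already used for acute pain in this department. It names the known side effects, "but no serious adverse events have been noted".
- II.d says "The research team will review safety information weekly". No independent board is named.

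**The concern.** A stopping rule should separate events that ought to end a study from events that ought to be recorded and watched. This one does not. Because II.a puts vomiting in the same list as life-threatening events, and II.e acts on any adverse event judged directly related, the two sections together make one related vomiting episode sufficient to halt the study.

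Neither reassurance in the protocol reaches the rule. Target size and patient volume say how fast the trial can recruit, not whether a related event will occur. The absence of serious events in past use does not help with a trigger that is not limited to serious events. Both arms receive ketamine, so every patient is exposed.

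What is at stake is completion and precision. A halted trial would compare the two doses on fewer than 49 per group. The rule also loads a large consequence onto a relatedness judgement for which no criteria are given, and that may discourage attributing minor events to the study.

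**Working it through.** **Step 1: the wording.** Taking II.a and II.e together:

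- Trigger (II.e): one adverse event judged directly related to participation.
- Events that II.a calls adverse events: hypoxia below 90%, systolic pressure below 90, vomiting, life-threatening events.
- Count or seriousness condition: none in II.e, and nothing elsewhere in the protocol adds one.

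So one related non-serious listed event meets the condition for an immediate stop. This step needs no assumed rate.

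**Step 2: planned size.** 49 per group at 1:1 allocation gives 49 × 2 = 98. The 49 itself cannot be re-derived, because no effect size, standard deviation, power or event rate is given. The point does not depend on it.

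**Step 3: how much room the rule leaves.** Let p be the chance, per patient, of a listed event judged directly related to participation. The documents give no value, so every p below is an assumption. With independent patients and constant p, P(98 patients with no trigger) = (1-p)^98.

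| Assumed p | Calculation | Chance of completing |
|---|---|---|
| 0.1% | 0.999^98 | 91% |
| 0.5% | 0.995^98 | 61% |
| 1% | 0.99^98 | 37% |
| 2% | 0.98^98 | 14% |

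Counting only the first 97 patients (a stop before the last enrolment) changes these by less than half a percentage point.

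Turned round, the largest p that allows a completion chance t is 1 - t^(1/98):

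- t = 90%: p = 0.11% (about 1 patient in 931)
- t = 80%: p = 0.23% (about 1 in 440)
- t = 50%: p = 0.70% (about 1 in 142)

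**Step 4: precision if a stop did occur.** At an assumed p of 1%, and given that the rule fires, the mean number enrolled is the sum of k·p·(1-p)^(k-1) over k = 1 to 98, divided by 1-(1-p)^98. This is about 42. With equal allocation and the same standard deviation, the interval for the dose difference would be √(98/42) ≈ 1.5 times as wide as with 98 patients. This figure is conditional on both the assumed rate and an early stop.

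**Step 5: effect of changing the rule.** If a share s of related listed events is serious (also assumed), the chance of no immediate stop becomes (1-p·s)^98.

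| s | p = 1% | p = 2% |
|---|---|---|
| 10% | 91% | 82% |
| 50% | 61% | 37% |
| Rule as written | 37% | 14% |

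For a pause count, take three related events as an example. The binomial chance of reaching three among 98 patients is 7.6% at p = 1%, 31.2% at 2% and 87.3% at 5%. The chance of at least one, which triggers the present rule, is 62.7%, 86.2% and 99.3%.

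**The case against.** The strongest reply is that the trigger is narrower than it looks. II.e speaks of relatedness to participation, not to ketamine. Both study doses lie within the 0.1 to 0.3 mg/kg range that II.b describes as current practice, under the same monitoring guidelines. A team could reasonably regard vomiting after such a dose as a known drug effect and not a consequence of being in the study. That stands as a possible reading, and it means p could be near zero. It does not settle the matter: participation is what fixes the patient's dose, and the text does not exclude drug effects. On the narrow reading the rule would also rarely fire even for a serious ketamine reaction, which is hardly its purpose.

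A second reply is that the wording is loose and no hair-trigger was intended. The survey description in I.d uses 'adverse effect' and 'adverse event' interchangeably, and the II.a heading suggests that the second list may have been meant as the serious tier. If so, II.b's reassurance would apply to it. This also has force, but II.a does not say so, and vomiting would still be a trigger.

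A third reply is that a very cautious rule is a legitimate choice for the sponsor and ethics board. That is true. The rule introduces no bias or analysis error by itself. The issue is whether halting on one non-serious event was intended.

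A reader might go further and infer that the trial is likely to stop early, that common effects such as dizziness or nausea would end it, or that any stop would be permanent. The documents support none of these. They give no event rate. II.a puts dizziness, disorientation, dysphoria and nausea in a separate list of effects. II.e does not say whether a stopped study may resume.

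**Conclusion.** The point holds as a statement about the rule. Read as written, II.a and II.e let one related non-serious event, such as vomiting, halt the study before 98 patients. That rests on the text alone.

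The probability of it happening is unknown. It depends on an event rate that the protocol does not state and on how the team interprets relatedness to participation. The completion figures (91% at 0.1%, 37% at 1%) assume independent patients and a constant rate. They show how little margin the rule leaves, not what will happen. The precision loss is likewise illustrative. This is a stated rule that works badly if followed, and it is worth correcting because the correction is cheap.

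**What to change.** Amend II.e and II.a as follows:

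- **Immediate stop:** a single life-threatening or otherwise serious adverse event judged related to the study drug or study procedures. Naming both removes the ambiguity about participation.
- **Related non-serious events** (vomiting, transient hypoxia or hypotension): report them to the existing weekly review in II.d, with a count fixed in advance at which enrolment pauses. Without a count, repeated related hypoxia or hypotension would never reach a stated threshold.
- **II.a:** mark which listed events are serious.
- **Resumption:** state whether enrolment may resume after a stop or pause, and following what review.

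The sponsor and ethics board should choose the count, ideally against an expected event rate. A count of three would seldom be reached at an assumed 1% rate but usually would be at 5%.

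The cost is a protocol amendment with ethics board review. It needs no extra patients, visits or staff for the weekly review, which already exists. The downside is that the trial continues after isolated related non-serious events.
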